### WP3: Collection and analysis of existing/routine quantitative data sets on the scale and scope of locum working in primary and secondary care (RQ1)

There are some existing routine data sets in both primary and secondary care which have not yet been used to analyse patterns of locum working/usage and how they have changed over time. While these routine data sources have some limitations, which we outline below, we think it is important to use them to provide a more definitive and comprehensive picture of locum working in the NHS in England.

#### Primary care

Since 2015, NHS Digital has produced a quarterly dataset on the general practice workforce.(42) Data are produced from practice submissions which are voluntary but coverage is high, for example only 5.7% of practices were not included in the most recent release (September 2018) due to incomplete submissions. The completeness of locum data declarations has been examined by NHS Digital and adjusted to ensure that short-term as well as long-term locum staff are being included in practice submissions.(43)These data will

be used to describe characteristics of the locum workforce compared to the non-locum GP workforce.

There are currently 13 quarterly time points available from September 2015 to March 2019. We expect the analysis to include up to March 2021 which should be released in May 2021, a total of 21 time points. Within each General Practice Workforce release GPs are categorised as GP Partners, Salaried GPs, GP Registrars, GP Retainers or GP Locums. The last category is of primary interest and comparisons will be made to numbers of all GPs in the other categories.

The data reveal the number of GPs working in each practice by GP type and will be used to measure the count and proportion of locums working in each practice over time. Characteristics of these locums are not provided at the practice level to avoid possible re-identification of locums. We will supplement these data by linking practice level characteristics of interest (mentioned below). At the CCG level additional characteristics are provided. We can determine the headcount to Full Time Equivalent (FTE) ratio for locums, the gender composition of locums and the age provide of locums (in 5 year bands). These characteristics will be compared to other GP types and over time.

Descriptive analyses (descriptive statistics tables, heat maps and distribution plots) of these data will used to determine the following:

- 1. The current number of locums employed in GP practices and how this figure has changed from 2015 to 2021
- 2. The age and gender of the locum work force compared over time and compared to other types of GP
- 3. The geographical patterns in locum employment: including areas of high/low employment and employment in urban/rural areas

Regression analysis will be used to determine the association between locum employment and practice characteristics. The dependent variable for this analysis will be the proportion of locums employed at each practice. Independent variables will be important practice characteristic, specifically: size of patient population, age and gender composition of patient population, QOF performance, patient satisfaction, contract type, chronic condition disease registers, rural/urban location, local area deprivation and mean deprivation of patients registered with the practice.

These associations will be modelled using two approaches: (1) a single cross-section of the data from the most recent year available, and (2) a panel of all available data. The first approach will benefit from more variation in the dependent variable due to low locum use in the early years of the data, plus it will provide more contemporary findings. Multiple linear regressions models will be used here. The second approach will benefit from repeated observations per practice which can be used to model changes in locum use and practice characteristics over time. Multi-level (random or fixed effects) multiple linear regression models will be used here to account for clustering. Time will be modelled in quarterly bins.

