#### 4. Aims and Objectives

The overall aim of this research is to provide evidence on the extent, quality and safety of medical locum practice and the implications of medical locum working for health service organisation and delivery in primary and secondary care in the English NHS. Our three main research questions are:

**RQ1** – What is the nature, scale and scope of locum doctor working in the NHS in England? Why are locum doctors needed, what kinds of work do they undertake, and how is locum working organised? I RQ2 - How may locum doctor working arrangements affect patient safety and the quality of care? What are the mechanisms or factors which may lead to variations in safety /quality between locum and permanent doctors? What strategies or systems do organisations use to assure and improve safety and quality in locum practice? How do locum doctors themselves seek to assure and improve the quality and safety of their practice? I RQ3 – How do the clinical practice and performance of locum and permanent doctors compare? What differences in practice and performance exist and what consequences may they have for patient safety and quality of care?

This research is grounded in three main existing bodies of literature/theory which we have used to plan and frame our proposed empirical work: that related to temporary workers in organisations and the causes/consequences of precarious employment;(29-31) the wider literature on the sociology of the medical profession and particularly theories concerned with restratification and intraprofessional hierarchy and the nature and construction of professional identity; (32-34) and theories concerned with social identity and intergroup

relations, group identity and behaviours.(35, 36). The peripatetic nature of locum working may mean that locums practice on the periphery of healthcare organisations and of the profession, and may consequently have a weaker connection to organisational and professional norms and values. This raises questions about how locum doctors' professional autonomy and identity is constructed and legitimised relationally, how group identities and intergroup relationships are constructed and enacted, and the nature of intraprofessional group relationships and behaviours.

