Our recent international review of the literature on locum working (17) identified eight key factors through which locum working may affect the quality and safety of patient care and which may also provide the basis for mechanisms or interventions designed to improve the quality and safety of locum working. These factors are summarised in table 1, and we plan to use this framework to structure and guide our fieldwork and analysis.

Theme	Theme description
Governance and patient safety	Locums are on the fringes of governance. Gaps in the oversight of locums continue to be a
	patient safety risk e.g. background checks. The short-term nature of locum work means that
	locums are less likely to take part in clinical governance activities, such as audits and
	continuing professional development (CPD).
Policies, procedures and continuity of	Locums are less likely to be aware of contextual issues and local policies and procedures that
care	are relevant to providing safe and effective care, especially if they do not receive adequate
	induction and briefing when they take up a locum role in a new/unfamiliar organisation.
	Locums are not prepared for practise in the same way as permanent staff – for example,
	inductions are often poor or absent meaning locums are unable to carry out their duties
	safely and efficiently. Other risks include not knowing how to escalate concerns, and being
	placed in challenging environments where staffing is an issue. Procedures may be less likely
	to be carried out when a locum is on duty. The use of locums presents a patient safety issue
	and may have a negative impact on continuity of care.
Impact on the healthcare team –	Locums (particularly short-term locums) can place burden on other members of the
scope of practice	healthcare team, such as nurses and junior doctors, who could be expected to perform
	outside of their scope of practice to compensate for a locum's lack of contextual/local
	knowledge/competencies.
Impact on the healthcare team –	Locum working can increase workload for other members of the healthcare team, for
workload	example, extra support for the locum who is unlikely to be familiar with policies and
	protocols and patients returning to see their regular GP.
Information exchange – patients	The quality and quantity of patient information may be reduced when locums are employed
	as locums are less likely to be familiar with the patient group and how to report and

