#### Secondary care

Since 2016, NHS Improvement has required all NHS trusts and foundation trusts to provide a weekly return detailing their use of locum medical staff, particularly high cost locums and adherence to locum pay caps. In addition, the three national procurement framework operators for NHS Improvement (Crown Commercial Services, Commercial Procurement Collaborative and Health Trust Europe) collect detailed information on all locum placements by suppliers registered on the framework through mandatory management information returns. This data has been used to produce some management statistics for NHS Improvement on locum usage/costs but otherwise has not been analysed to date. We have secured support and agreement in principle from NHS Improvement colleagues to us accessing this data, subject to necessary information governance approvals.

As the data are currently used by the NHS we believe the quality to be sufficient for our planned analyses. However, we will first need to undertake work to evaluate data quality and completeness over the period available, assessing the consistency of data definitions and their application and writing and applying code to clean data and check for data errors/inconsistencies. Any issues involving quality or completeness will be fed back to NHS Improvement so the data may be corrected for future releases.

We will then link data to available trust-level characteristics of interest, such as bed availability/occupancy and CQC inspection ratings, as well as using published aggregated Hospital Episode Statistics (HES) data on inpatient and outpatient activity by specialty and month/year. We will produce descriptive analyses of variations in locum usage by specialty, trust type and geographic area over time. We will use regression analysis (mirroring the approach described for primary care) to examine associations between locum usage and specialty/trust characteristics.

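### WP3 adjusts deprivation and rurality for QOF performance and patient satisfaction, so its coefficients do not give the overall gradients in locum use, and the two quality coefficients have no direction

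*Protocol*

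**What the plan says.** The aim is given in Protocol section 5, WP3, Primary care: "Regression analysis will be used to determine the association between locum employment and practice characteristics". The outcome is fixed next: "The dependent variable for this analysis will be the proportion of locums employed at each practice". The independent variables are then named as a specific set: size and age and gender mix of the patient population, then "QOF performance, patient satisfaction, contract type, chronic condition disease registers, rural/urban location, local area deprivation", and finally the mean deprivation of registered patients.

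Two models follow. For the most recent single year: "Multiple linear regressions models will be used here". For the panel in quarterly bins: "Multi-level (random or fixed effects) multiple linear regression models will be used here to account for clustering". The text mentions no lag for QOF or satisfaction, no staged entry, and no model without them.

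The WP3 Secondary care text says that its regressions will mirror this approach. It gives "bed availability/occupancy and CQC inspection ratings" as examples of the trust characteristics to be linked.

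Section 4 considers the opposite direction. RQ2 asks "How may locum doctor working arrangements affect patient safety and the quality of care", and the framework in Table 1 is introduced as "eight key factors through which locum working may affect the quality and safety of patient care".

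**The concern.** A reader will use WP3 to learn which kinds of practice rely on locums, for example whether deprived or rural practices use more. In a mutually adjusted model, the deprivation coefficient compares practices with the same QOF score and the same patient satisfaction. If those two measures are partly a result of locum use, the model conditions on a consequence of its own dependent variable, and the structural coefficients absorb a bias. The coefficients of QOF and satisfaction are also hard to read, because a same-period association cannot show whether low satisfaction goes with needing locums or follows from using them.

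Deprivation is the most exposed. The descriptive analyses listed for primary care cover geography and urban/rural location but do not name deprivation, so this regression is the only stated WP3 primary care analysis of the deprivation gradient.

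**Working it through.** The protocol gives no effect size or sample size for this regression, so there is no stated figure to reproduce. Every effect below is an assumption on a standardised scale. D is deprivation, L is locum share and S is a quality measure such as QOF or satisfaction.

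**Direction 1: locum use affects S.** Let D→L = d and S = aD + bL + error. Then

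- correlation of D and S: r_DS = a + bd
- correlation of L and S: r_LS = b + ad
- coefficient of D on L, adjusted for S: (d − r_DS·r_LS) / (1 − r_DS²)

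Without S in the model the coefficient is d. With d = 0.20:

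| a (D→S) | b (L→S) | Calculation | Adjusted coefficient | Change from 0.20 |
|---|---|---|---|---|
| −0.30 | −0.30 | (0.20 − 0.1296)/(1 − 0.1296) | 0.081 | −60% |
| −0.20 | −0.20 | (0.20 − 0.0576)/(1 − 0.0576) | 0.151 | −24% |
| −0.10 | −0.10 | (0.20 − 0.0144)/(1 − 0.0144) | 0.188 | −6% |
| 0 | −0.30 | (0.20 − 0.0180)/(1 − 0.0036) | 0.183 | −9% |
| +0.30 | −0.30 | (0.20 + 0.0576)/(1 − 0.0576) | 0.273 | +37% |

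Three things follow. If b = 0 there is no change. If b is not zero but D has no direct relation to S, the change is small (9% at b = −0.30). The sign of a decides whether the gradient shrinks or grows. With a weaker true gradient, d = 0.10 and a = b = −0.30, the result is (0.10 − 0.1089)/(1 − 0.1089) = −0.01, so the gradient vanishes. A simulation of 1,000,000 practices per setting agreed with the formula in the settings with a zero or negative.

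**Direction 2: S affects locum use.** Let the direct effect of D on L be g, S→L = h and D→S = a. The overall association is g + ha. The adjusted coefficient is g, so the part ha is removed.

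- g = 0.20, h = −0.10, a = −0.20: overall 0.20 + 0.02 = 0.22, adjusted 0.20 (−9%)
- g = 0.20, h = −0.30, a = −0.30: overall 0.20 + 0.09 = 0.29, adjusted 0.20 (−31%)
- g = 0.10, h = −0.30, a = −0.30: overall 0.10 + 0.09 = 0.19, adjusted 0.10 (−47%)
- a = 0: no change

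Here the adjusted coefficient is unbiased for the direct association, but it is still not the overall one.

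The same algebra applies with rurality in place of D. The documents give no basis for a separate size.

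**The case against.** The strongest reply is that WP3 serves RQ1 and claims only associations. For a descriptive aim, a mutually adjusted coefficient is a legitimate conditional association, and the protocol nowhere says that QOF or satisfaction will be read as drivers of locum use. This stands, and it is why the plan is not wrong in itself. It does not say which association is wanted, and the conditional one does not answer which practices use more locums overall.

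A reader might infer more than the text supports in four ways.

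- That the protocol expects locum use to lower quality. RQ2 and the framework mostly say that it may. One line of Table 1 is firmer on patient safety, but section 2 concludes that the evidence for such assumptions is limited.
- That harm to QOF or satisfaction is part of the stated theory. Section 4 names neither. The nearest text, in section 2, is that patients often perceive locums negatively, which is not practice-level satisfaction.
- That the gradients are distorted, and always towards zero. This needs a non-zero effect of locum use on the measures, and the sign can go either way. Section 2 also supports the reverse direction, since locums fill gaps left by recruitment problems and in underserved areas.
- That the hospital model is fixed with CQC rating as a covariate. It appears only as an example of data to be linked.

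Two further replies carry some weight. Urban/rural patterns will be described outside the regression, which limits the loss for rurality but not for deprivation. Staged entry or lags could also be set out in an analysis plan that is not at hand. Against this, the protocol itself names the covariates as a specific list, so the choice is made here.

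**Conclusion.** The point holds in a limited form. Under either causal direction, the model as described does not report the overall association of deprivation or rurality with locum use whenever these characteristics and locum use are both related to the quality measures. The QOF and satisfaction coefficients cannot be given a direction. How much this matters cannot be known from the protocol: the range of 0.08 to 0.27 around an assumed 0.20 is illustrative, and the difference is nil or small where the links are absent or weak. It is a cheap improvement to how the model is reported, not an error that invalidates WP3.

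**What to change.** In section 5, WP3, Primary care, present the regression in two steps:

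1. Structural characteristics only: list size, age and gender mix, disease registers, contract type, rurality and deprivation. Report these coefficients as the gradients in locum use.
2. Add QOF performance and patient satisfaction, lagged in the panel where possible, and state that these associations are of uncertain direction. A lag helps with ordering in time but does not settle direction if locum use persists from year to year.

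In WP3, Secondary care, do the same if CQC rating is used as a covariate. Modelling quality as an outcome of earlier locum share would go beyond RQ1 and is optional.

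The cost is a few sentences and one further set of models on the same data. The structural model will explain somewhat less variance, which does no harm for this purpose.

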All outcomes and key covariates of interest will be appropriately described over time, at the patient, GP and general practice level. For example, we will plot the percentage of revisits within 7 days by locum/permanent GP groups, across all practices, over time. We will use multi-level mixed effects logistic regression models to quantify the association between the exposure of interest (locum/permanent GP) and the outcomes of interest, controlling for all available covariates previously discussed. If an outcome (e.g. safety indicators) in better expressed as a count, e.g. if we identify that numerous indicators tend to apply to visits, we will use multi-level mixed effects Poisson or negative binomial regression models instead. Analyses will be conducted at the patient level, accounting for the nested structure of the data: patients within general practices, within regions. We will include random effects for practices and possibly for regions (alternatively a fixed effect for regions).

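### The WP3 practice regressions name no area level, so standard errors for rurality and deprivation may be too small if locum use stays correlated within areas

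*Protocol*

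**What the plan says.** The regression part of Protocol section 5, WP3, Primary care fixes the outcome: "The dependent variable for this analysis will be the proportion of locums employed at each practice". The covariates are given as a specific list that ends with "rural/urban location, local area deprivation and mean deprivation of patients registered with the practice"; neither region nor CCG is on it.

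Two approaches follow, each with its own model:

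- Approach 1 uses "a single cross-section of the data from the most recent year available", and for it "Multiple linear regressions models will be used here".
- Approach 2 uses the full panel: "Multi-level (random or fixed effects) multiple linear regression models will be used here to account for clustering". The sentence before it speaks of repeated observations on each practice. No area level is named.

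Earlier in the same section, the third descriptive aim is "The geographical patterns in locum employment: including areas of high/low employment and employment in urban/rural areas". The section also shows that an area grouping is at hand: "At the CCG level additional characteristics are provided".

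WP4, Primary care, lists region among the practice covariates and describes its models as "accounting for the nested structure of the data: patients within general practices, within regions", with a random or fixed effect for region.

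**The concern.** Multiple linear regression with conventional standard errors treats practices as independent once the covariates are in the model. Practices in one area draw on the same local supply of doctors and may resemble each other in locum use for reasons that the covariates do not capture. The study itself makes geographical patterning of locum use a question.

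The covariates most exposed are those that also cluster by area: rural/urban location and the two deprivation measures. When both the residual and the covariate are positively correlated within areas, the conventional standard error understates the uncertainty. Confidence intervals come out too narrow and p-values too small. A covariate that varies freely between neighbouring practices is little affected.

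At stake is whether an association of locum use with rurality or deprivation is reported with more certainty than the data carry. WP3, Secondary care says that its regressions will mirror the primary care approach, so the same gap may pass to the trust-level models.

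**Working it through.** **Figure to reproduce.** There is none. The protocol gives no sample size, significance level, standard error or intra-area correlation for WP3.

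**Inputs.** From the protocol: the practice-level outcome, linear regression, no area term, and the three area-type covariates. Assumed, because the protocol is silent:

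- m, practices per CCG: 35, varied from 10 to 50
- rho_y, correlation of locum share within areas *after* adjustment: 0 to 0.10
- rho_x, correlation of the covariate within areas: 0.2 to 0.8
- a two-sided 5% test

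**Formula.** Moulton variance inflation, with equal area sizes:

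VIF = 1 + (m − 1) × rho_y × rho_x

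True rejection rate under the null = 2 × [1 − Φ(1.96 / √VIF)]

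**Worked cases, m = 35.**

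- rho_y = 0.01, rho_x = 0.2: VIF = 1 + 34 × 0.002 = 1.07, rejection 5.8%
- rho_y = 0.01, rho_x = 0.8: VIF = 1 + 34 × 0.008 = 1.27, rejection 8.2%
- rho_y = 0.05, rho_x = 0.2: VIF = 1 + 34 × 0.010 = 1.34, √VIF = 1.16, rejection 9.0%
- rho_y = 0.05, rho_x = 0.8: VIF = 1 + 34 × 0.040 = 2.36, √VIF = 1.54, rejection 20.2%

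**Rejection rate of a nominal 5% test, m = 35.**

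| Residual rho_y | rho_x = 0.2 | rho_x = 0.5 | rho_x = 0.8 |
|---|---|---|---|
| 0 | 5.0% | 5.0% | 5.0% |
| 0.01 | 5.8% | 7.0% | 8.2% |
| 0.05 | 9.0% | 15.0% | 20.2% |
| 0.10 | 13.0% | 23.3% | 31.0% |

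**Sensitivity to m.** At rho_y = 0.05, the range over rho_x = 0.2 to 0.8 is 7.2% to 14.0% for m = 20 and 10.8% to 25.5% for m = 50. Over m = 10 to 50, rho_y = 0.01 to 0.10 and rho_x = 0.2 to 0.8, the full span is 5.2% to 37.7%.

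**Check by simulation.** 190 areas of 35 practices, 1,500 runs per setting, no true association. One standard error of a 5% rate is √(0.05 × 0.95 / 1500), about 0.6 percentage points.

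| rho_y, rho_x | Ordinary standard errors | Area-clustered standard errors |
|---|---|---|
| 0, 0.5 | 4.5% | 4.7% |
| 0.01, 0.5 | 7.7% | 5.7% |
| 0.05, 0.2 | 8.3% | 5.0% |
| 0.05, 0.5 | 15.8% | 6.1% |
| 0.05, 0.8 | 21.1% | 6.3% |
| 0.10, 0.8 | 30.5% | 5.7% |

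The simulation agrees with the formula. Over all twelve settings run, area-clustered errors held the rate at about 4.5% to 6.3%.

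**The case against.** The best defence is that the protocol names a model family, not a variance estimator. Area-clustered standard errors are compatible with multiple linear regression, and that detail may sit in an analysis plan that is not shown. WP3 states no hypothesis test and no significance level; it serves a descriptive research question. The adjustment set already holds rurality, two deprivation measures, patient age and sex mix and disease registers, any of which may absorb much of the likeness between neighbouring practices.

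Part of this stands. It is why the point is conditional and modest. It does not dispose of it: the section does address clustering, but only for the panel and beside the reference to repeated practice observations. The covariate list is closed without an area term, while WP4 carries one.

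Four stronger readings are tempting, and the protocol does not support them:

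- *That significance is certainly overstated.* This needs correlation left over after adjustment, for which no figure is given. At zero there is no inflation at all.
- *That the authors expect strong area clustering.* They plan to describe high and low areas, and give no evidence on how strongly locum use clusters.
- *That the coefficients are biased, and clustered errors would cure it.* Correlated errors alone do not bias the coefficients. Confounding by local labour supply is a separate question; clustered standard errors do not remove it, and a random intercept or region term would do so only in part.
- *That WP4 contradicts WP3.* WP4 analyses patients and asks another question. It shows that the team models region elsewhere, no more.

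**Conclusion.** The point holds in conditional form. Neither WP3 primary care model, as written, protects against correlation between practices in the same area, although the study sets out to look for just that pattern. The gap is not peculiar to the cross-section, since the panel names no area level either.

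The consequence runs from none to material, depending on a residual correlation that cannot be known from the protocol. On the assumption of 35 practices per CCG, a residual value of 0.01 does little harm, whereas 0.05 would make the true standard errors of area-type covariates 1.16 to 1.54 times those reported. It touches inference on rurality and deprivation in an association analysis, not the WP4 comparison of locum and permanent doctors. It is a minor improvement, worth making because it is nearly free.

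**What to change.** In the regression part of section 5, WP3, Primary care, state for both approaches that inference allows for correlation within CCGs, by CCG-clustered standard errors or a CCG random intercept, and add a region term as WP4 does. If the panel is fitted with practice fixed effects, a constant CCG effect is already absorbed, so clustered standard errors at CCG level are the workable option there. Report the estimated intra-area correlation, so that readers can see whether it mattered. Say whether the secondary care regressions, which mirror this approach, carry an equivalent area term.

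The cost is a sentence or two of analysis wording and a CCG identifier on the practice records; no new data collection is needed. Intervals for rurality and deprivation would be somewhat wider. If residual area correlation is negligible, the results will hardly change. The revised text should not claim that clustering the standard errors deals with confounding by local labour supply.

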All analyses will be controlled for available patient, general practitioner and general practice characteristics. Patient: age, sex, deprivation as measured by the 2015 Index of Multiple Deprivation (IMD, in quintiles),(45) years registered with the practice (if not collinear with age), number of practice visits in the previous financial year (or in the previous 12 months since the current consultation event) and numerous chronic conditions which are well recorded in these databases since they are part of the Quality and Outcomes Framework (atrial fibrillation, asthma, cancer, coronary heart disease, chronic kidney disease, chronic obstructive pulmonary disease, dementia, depression, diabetes, epilepsy, heart failure, hypertension, limiting disabilities, severe mental health, osteoporosis, peripheral arterial disease, rheumatoid arthritis and stroke).(46) General practitioner: sex/age are unavailable, but see analytical plan below). General practice: list-size, urban/rural location, practice location IMD (in quintiles), region, ratio of locum consultations over total within the

respective analysis year. We will also derive and describe consultation characteristics, like type, length and day of the week, although these will be used for descriptive purposes.

Our power calculation is based on the primary outcome, revisiting general practice within 7 days, and on the assumption that 10% of patients consulting a permanent GP return within that time period. Assuming 9 consultations with a permanent GP for 1 consultation with a locum, an alpha level of 5%, and an increase in the outcome to 15% for locum consultations (OR=1.59), we would need a total of 4330 patients to have 90% power to detect the association. Although this approach ignores between-practice variability in both the intercept and the association (e.g. varying return rates for permanent GPs and locus), it does demonstrate that we have many hundreds (if not thousands) times the numbers needed to detect a meaningful association.

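### WP3 panel regression: a practice random or fixed effect alone does not protect tests on slowly changing practice characteristics if quarterly deviations are autocorrelated

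*Protocol*

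**What the plan says.** Protocol section 5, WP3, Primary care, plans regressions of locum use on practice characteristics. The outcome is set by "The dependent variable for this analysis will be the proportion of locums employed at each practice". There are two approaches. One uses "a single cross-section of the data from the most recent year available". The other is a panel of all available quarters, for which "Multi-level (random or fixed effects) multiple linear regression models will be used here to account for clustering", followed by "Time will be modelled in quarterly bins". On the length of the panel: "We expect the analysis to include up to March 2021 which should be released in May 2021, a total of 21 time points".

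The covariates are of two kinds. Some are fixed or nearly fixed for a practice, such as rural or urban location, contract type and area deprivation. Others can drift over time: list size, patient mix, QOF performance, patient satisfaction and disease registers. The stated advantage of the panel is that it can relate changes in locum use to changes in practice characteristics, so the time-varying coefficients are the ones it is meant to deliver.

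The Secondary care part of WP3 starts from weekly trust returns ("Since 2016, NHS Improvement has required all NHS trusts and foundation trusts to provide a weekly return detailing their use of locum medical staff") and says its regressions will follow the primary care approach.

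No residual correlation structure, type of standard error, significance level or power is stated for WP3. The 5% level in the document belongs to the WP4 power calculation.

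**The concern.** A practice intercept, random or fixed, allows for practices that are always high or always low. It implies the same correlation between any two quarters of a practice, and independence once that level is taken out. Locum use may not behave like that: the returns cover long-term as well as short-term locums, so a practice above its own average in one quarter may well still be above it in the next. If the covariate also moves slowly, high spells of one can line up by chance with high spells of the other, and the model-based standard error does not allow for it.

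The risk is that changes in slowly moving characteristics are reported as associated with locum use when they are not, with intervals that are too narrow. The sentence on quarterly bins does not address this. It says how calendar time enters the mean model and does not bear on correlation between residuals. The sentence that matters is the one that names the practice effect as the way to handle clustering.

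**Working it through.** WP3 states no error rate, so there is no figure of the plan's own to reproduce. The check is of type I error.

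**Inputs.** From the protocol: T = 21 quarters; a linear model with a practice effect. Assumed: two-sided 5% test; residual autocorrelation ρ from 0 to 0.9; a covariate updated once a year with year-to-year correlation 0.8; no true association; quarter effects removed.

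**Model.** y_it = a_i + g_t + βx_it + e_it, with β = 0 and e_it = ρe_i,t−1 + u_it.

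**Closed form for fixed effects.** Let M be the matrix that removes the practice mean, Ω_e the correlation matrix of the residuals over the 21 quarters, and Ω_x that of the covariate. Put A = MΩ_eM and B = MΩ_xM. The true variance of the estimate divided by its model-based variance is

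VR = tr(AB) / [ tr(A)/(T−1) × tr(B) ]

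The rejection rate is 2[1 − Φ(1.96/√VR)]. The number of practices cancels. At ρ = 0.5, VR = 2.368, √VR = 1.539, 1.96/1.539 = 1.274, and the rejection rate is 20.3%.

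**Simulation.** 500 practices (assumed), practice and residual SD both 1, 2,000 replicates.

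| ρ | VR | √VR | Fixed effects, closed form | Fixed effects, simulated | Random intercept, simulated | Fixed effects, clustered SE |
|---|---|---|---|---|---|---|
| 0 | 1.000 | 1.00 | 5.0% | 4.5% | 4.9% | 5.0% |
| 0.3 | 1.645 | 1.28 | 12.6% | 12.4% | 11.4% | 5.3% |
| 0.5 | 2.368 | 1.54 | 20.3% | 19.2% | 17.5% | 5.4% |
| 0.7 | 3.577 | 1.89 | 30.0% | 29.8% | 26.6% | 5.2% |
| 0.9 | 5.699 | 2.39 | 41.2% | 39.8% | 37.5% | 4.8% |

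**Sensitivity.**
- A second simulation (500 practices, annual covariate) gave fixed-effects rates of 5, 10, 14, 21, 32 and 45% at ρ = 0, 0.2, 0.3, 0.5, 0.7 and 0.9, against 5 to 7% with clustered standard errors.
- With 1,000 practices, a less persistent annual covariate (year-to-year 0.5) and 400 replicates, the rates were 17, 29 and 35% at ρ = 0.5, 0.7 and 0.9.
- A covariate that follows its own quarterly autoregression at 0.9 gave 12.0, 19.8, 29.4 and 39.2% at ρ = 0.3, 0.5, 0.7 and 0.9.
- A covariate with no serial correlation beyond its practice mean gave 4.4 to 5.6% under both models.
- An unbroken quarterly count from September 2015 to March 2021 is 23. With T = 23 the closed form gives 13.0% at ρ = 0.3 and 42.7% at 0.9, so the count does not matter here.

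**Time-invariant covariate.** The random intercept rejects 5.7, 4.8, 5.1, 5.0 and 5.2% at ρ = 0, 0.3, 0.5, 0.7 and 0.9. Fixed effects cannot estimate such a coefficient.

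**Clustered standard errors.** In the 2,000-replicate simulation, across all covariate types and both models, rejection lay between 3.4 and 6.2%.

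**The case against.** The strongest reply is that the protocol names a class of model and is silent on the variance estimator. Clustered standard errors fit within its wording, and an analysis plan that is not at hand may specify them. This stands in part: the protocol excludes nothing. But it does name its device for repeated quarters and the purpose of that device, and the device alone is not enough for the time-varying coefficients that justify the panel. The point is that a better method is available at almost no cost, not that a detail is missing.

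A reader might also infer more than the document supports:
- *That practice effects treat successive quarters as independent.* They do not. They model a common correlation within practice, and independence holds only given the practice effect. Full independence would be pooled least squares, which the protocol does not propose; for a time-invariant covariate it rejected 56 to 63% of the time.
- *That all persistent characteristics are affected.* The most persistent ones, such as location, are not: a random intercept keeps its level and fixed effects drop them.
- *That inflation is certain.* It needs serial correlation in both residual and covariate, and the protocol gives neither.
- *That the secondary care models are worse because their records are weekly.* The returns are weekly, but the unit of the regression is not stated and aggregation is possible. If 200 trusts with 208 weekly records each were analysed as such (assumed), fixed effects would reject 26, 41 and 63% at weekly ρ of 0.5, 0.7 and 0.9 for a covariate updated yearly, and trust-clustered standard errors 4 to 8%. That remains conditional.

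Finally, WP3 is descriptive and associational with no decision rule, and the cross-section offers a separate view. This limits the consequences but does not repair the panel tests.

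**Conclusion.** The point holds in conditional form. If quarterly deviations within a practice are autocorrelated and model-based standard errors are used, the practice effect alone gives standard errors that are too small for slowly time-varying characteristics. For an annually updated covariate under fixed effects, the true standard error is about 1.3 times the reported one at an autocorrelation of 0.3 and about 2.4 times at 0.9. Across the two 500-practice simulations that is a rejection rate of 12 to 14% and 40 to 45% respectively, instead of 5%; a less persistent covariate gives somewhat lower rates at high autocorrelation. Random intercepts are only slightly better. At zero autocorrelation there is no inflation.

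Time-invariant characteristics under a random intercept are unaffected, as is the cross-section provided it uses one record per practice. The size rests on the assumed autocorrelation and covariate persistence, neither of which the protocol gives. The number of practices has no bearing on it.

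**What to change.** In section 5, WP3, Primary care, directly after the sentence on multi-level models, state that inference from the panel models uses standard errors clustered by practice, optionally with an autoregressive within-practice residual. Make clear that the practice effect is not by itself the adjustment for repeated quarters. In the Secondary care part, state that the parallel models use standard errors clustered by trust, whatever time unit is chosen.

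This needs no new data: one sentence in each place and one software option. Where autocorrelation is absent the test keeps its level. Where it is present, intervals for time-varying coefficients widen, by a factor of about 1.3 to 2.4 over autocorrelations of 0.3 to 0.9 in the annual-covariate case above. That widening is the uncertainty the model-based intervals would have left out.
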